**Table 1: Study Visits**

Study Period	Screening & Run-in		Treatment Period (Visits 1 -10)										Follow-up
	S1	S2/3	V1 DoR	V2	V3	V4	V5 Phone	V6	V7	V8	V9	V10 EOT	
Week	-5		0	2	4	6	7	8	10	12	14	16	24
Study Day	-		1	15	29	43	50	57	71	85	99	113	169

DoR=Day of Randomization; EOT=End of Treatment; EOS=End of Study.

‘Last Assessment’ may be derived for analysis purpose and is defined as the last observed postbaseline data during the treatment period. For patients who withdraw from the study early, their data at the early withdrawal visit will be excluded from the by-visit summaries but will be included in the Last Assessment summaries.

Study days are numbered relative to the first day of the IMP administration. The start of treatment (day 1) is defined as the date on which a patient takes the first dose of the IMP, as recorded on the case report form (CRF). Days will be numbered relative to treatment start (ie, ..., -2, -1, 1, 2, ...; with day 1 being the first day of the IMP administration and day -1 being the day before the first day of the IMP administration).

## 5. STUDY POPULATION

### 5.1. General

The ITT analysis set (see Section 3.1) will be used for all study population summaries unless otherwise specified. Summaries will be presented by treatment group and all patients. All data will be listed and sorted by treatment group and subject identifying number.

### 5.2. Patient Disposition

Data from patients screened, patients screened but not randomized, patients randomized to treatment in the study, patients randomized but not treated, patients in the safety analysis set, patients in the per-protocol analysis set, patients who completed the treatment period (week 16), patients who completed the study (see Section 2.1 for definition of study completion), and patients who did not complete treatment but were followed up until end of study will be summarized. Data from screen failures, patients who did not complete the treatment period and patients who did not complete the study will also be summarized by reason for withdrawal using descriptive statistics.

This summary will include all patients.

### 5.3. Demographics and Baseline Characteristics

The demographic data will be collected at the screening visit after the patient signs the informed consent form. Patient demographic data including age, age group (<65 years vs ≥65 years), gender, race, race group (white or other), ethnicity, baseline weight (kg), baseline weight group (<75 kg vs ≥75 kg), baseline height (cm), baseline body mass index (BMI; kg/m^2), and baseline BMI group (<30 vs ≥30) will be summarized using descriptive statistics for the ITT, safety and PP analysis sets.

Baseline characteristics including asthma history and ECG findings at screening will be summarized for the ITT analysis set using descriptive statistics. No inferential analyses will be performed.

Asthma history includes

- Months since asthma diagnosis
- The duration of asthma
- The number of inpatient hospitalization due to asthma over the past 12 months
- Months since most recent inpatient event
- The number of emergency department visit due to asthma over the past 12 months
- Months since most recent emergency department visit
- the number of times oral corticosteroids were prescribed for asthma in the last 18 months
- Months since last prescription of corticosteroids

The month will be calculated as (date of informed consent - the date of the event + 1)/30.44. Rules for handling partial dates are in Section 4.3.

#### **5.4. Medical History**

All medical history abnormalities will be coded using the Medical Dictionary for Regulatory Activities (MedDRA). The incidence of medical history abnormalities will be summarized using descriptive statistics by system organ class (SOC) and preferred term. Patients are counted only once in each SOC and only once in each preferred term.

#### **5.5. Prior Therapy and Medication**

All prior medications or therapy will be coded using the World Health Organization Drug Dictionary of medical codes (WHO Drug). The incidence of prior medications or therapy will be summarized by therapeutic class and preferred term using descriptive statistics. Patients are counted only once in each therapeutic class category, and only once in each preferred term category. Prior medications will include all medications taken prior to the administration of the first dose of the IMP.

#### **5.6. Childbearing Potential and Methods of Contraception**

Information related to reproductive system findings will be collected at the screening visit. Data will be listed.

#### **5.7. Physical Examinations**

Patients with at least 1 abnormal finding (overall) and abnormal findings for each category at the baseline will be summarized and listed.

#### **5.8. Study Protocol Deviations**

Data from patients with any important protocol deviations during the study will be summarized overall and for each category using descriptive statistics. All study protocol deviations will be listed.

## 6. EFFICACY ANALYSIS

### 6.1. General

The ITT analysis set (Section 3.1) will be used for all efficacy analyses unless otherwise noted. Summaries will be presented by treatment group. The mITT and per-protocol analysis sets (Section 3.4) will be used as supplementary analysis for the primary analysis. All efficacy related data will be listed using ITT analysis set unless otherwise specified.

The baseline for clinic visit variables will be the last observed value before the first dose of study drug.

The baseline for spirometry parameters and e-diary variables will be based on the daily average of the values over the 7 days preceding day of randomization.

#### 6.1.1. Analysis Windows for E-diary Data

For the purpose of analysis, the analysis windows for the treatment period will be derived for data collected on e-diary and with hand-held spirometry daily if applicable.

**Postbaseline monthly (4-week) analysis windows during the treatment period** will be determined based on the actual dosing day as follows:

- Month 1/Weeks 1 to 4: from the day of 1st IMP administration to the day before 3rd IMP administration (visit 3/week 4 dosing);
- Month 2/Weeks 5 to 8: from the 3rd IMP administration (visit 3/week 4 dosing) to the day before the 5th IMP administration (visit 6/week 8);  
Note, Visit 5/Week 7 is a non-dosing visit.
- Month 3/Weeks 9 to 12: from the 5th IMP administration (visit 6/week 8) to the day before the 8th MP administration (visit 8/week 12);
- Month 4/Weeks 12 to 16: from the 8th IMP administration (visit 8/week 12) to the day of the EOT visit (visit 10/week 16);

Notes:

There will be no IMP administration at visit 10; for patients who withdraw from the study early, the end day for the last window will be the day before EOT/early termination (ET); a 4-week analysis window may contain <28, 28, or >28 days.

Postbaseline weekly analysis windows during the treatment period will be derived based on the study days as follows:

Week x: day  $(x-1)*7 + 1$  to day  $x*7$

Eg. Week 1 is study days 1 to 7; Week 2 is study days 8 to 14, etc.

**A post-treatment analysis window** will be from the day after the EOT visit to the day of the EOS visit (visit 11/week 24).

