7 weeks (Telephone, V5)	Second ICS decrease	250 decreased to 100 BID	100 BID decreased to 0
8 weeks (V6)	Third ICS decrease	100 BID decreased to 0	0

*Other asthma controllers (eg, LAMA, leukotriene antagonists) will also be discontinued.

Note: Last IMP administration 14 weeks after randomization (visit 9); end-of-treatment visit (EOT) 16 weeks after randomization

BID=twice daily; FP=fluticasone propionate; ICS=inhaled corticosteroids; LABA=long-acting beta-agonists; LAMA= long-acting muscarinic antagonist; V = visit.

Patients will be monitored for worsening of asthma and potential LoAC (and CAE) both at scheduled visits and in between visits via hand-held spirometry and e-diary. Asthma specific alerts will be sent for the following:

- Decrease in morning FEV₁ $\geq 20\%$ from baseline on 2 consecutive days OR decrease in morning PEF $\geq 30\%$ from baseline on 2 consecutive days
- Increase in rescue medication use/SABA of 4 or more puffs over baseline for 2 or more consecutive days OR ≥ 12 puffs in any single day
- Increase of 2 nighttime awakenings due to asthma over baseline on 2 consecutive days

In the event of an alert, the site will follow-up with the patient. An alert does not mean that the patient's medications need to be changed or that study drug should be discontinued, only that the patient should be contacted and evaluated by phone or at an unscheduled visit according to investigator judgment. If, in the investigator's judgment, LoAC is suspected, every effort to have the patient evaluated at an unscheduled visit should be made.

Definitions of LoAC and Clinical Asthma Exacerbation (CAE) are presented in Section 6.1.1 and Section 6.1.2. LoAC events and CAEs will be treated by the investigator according to local standard of care. In the event of a LoAC or CAE, IMP will be discontinued and background asthma controller therapy will be restarted or increased per investigator judgment. Patients who experience LoAC or CAE will remain in the study for assessments. (Note: CAEs are a subset of LoAC events; see Section 6.1.1 and Section 6.1.2 for definitions).

Study procedures and assessments are described in detail Section 3.6.

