### **8.2. Duration of Exposure to Study Drug**

The patients will receive the IMP loading dose on the day of randomization (visit 1) and the subsequent corresponding IMP maintenance dose every 2 weeks (visits 2 to 4 and visits 6 to 9) for a total of 8 doses ( [REDACTED] ).

Duration of the treatment period (days), the number of doses received, and reasons for IMP not administered (adverse event or other) will be summarized using descriptive statistics.

Duration of the treatment period (days) for a patient is defined as the number of days a patient is in the treatment period and calculated as the date of last IMP administration – the date of first IMP administration + 14.

IMP administration, IMP accountability data, and medical device malfunction data will be listed using safety analysis set.

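### SAP 6.1.1 ties the Month 3/Month 4 boundary to both the 8th dose and visit 8/week 12, but visit 8 is the 7th dose, so the two labels define different windows

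*SAP*

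**What the plan says.** SAP 6.1.1 states that the 4-week windows "will be determined based on the actual dosing day as follows". Month 2 runs "to the day before the 5 th IMP administration (visit 6/week 8"). Month 3 starts at that dose and runs "to the day before the 8 th MP administration (visit 8/week 12"). The last window is defined as "Month 4/Weeks 12 to 16: from the 8 th IMP administration (visit 8/week 12") "to the day of the EOT visit (visit 10/week 16"). The section also records: "Note, Visit 5/Week 7 is a non-dosing visit". It says that there is no dose at visit 10 and that a window may be shorter or longer than 28 days.

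The dosing schedule is given elsewhere. SAP 8.2 puts the loading dose at visit 1 and the maintenance doses "every 2 weeks (visits 2 to 4 and visits 6 to 9) for a total of 8 doses". The note to protocol Table 1 (section 3.1) reads: "Note: Last IMP administration 14 weeks after randomization (visit 9").

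**The concern.** The Month 3/Month 4 boundary is identified twice, once by dose number and once by visit, and the two do not fall on the same day. The governing rule points to dosing days, so a programmer has a textual reason to follow the ordinal. The heading and labels give another programmer equal reason to follow the visit.

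The windows feed several analyses: SABA use (key secondary, MMRM and EOT; SAP 6.3.4), nighttime awakenings (6.4.3), ICS dose (6.4.4) and hand-held FEV1 and PEF (6.4.5). For SABA and hand-held spirometry, patients who do not complete treatment take their EOT value from their last window. If completers' EOT value is Month 4, which the SAP implies but does not state, its content depends on which label is used.

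Ordinals also assume that no dose is missed. SAP 6.1.1 has a note for early withdrawal, but no rule for a patient who skips a dose and carries on.

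**Working it through.** **Inputs.** Dosing visits are V1, V2-V4 and V6-V9 (SAP 8.2). V5 and V10 carry no dose (SAP 6.1.1). Nominal study days come from SAP Table 1.

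| Dose | Visit | Week | Day |
|---|---|---|---|
| 1 | V1 | 0 | 1 |
| 2 | V2 | 2 | 15 |
| 3 | V3 | 4 | 29 |
| 4 | V4 | 6 | 43 |
| 5 | V6 | 8 | 57 |
| 6 | V7 | 10 | 71 |
| 7 | V8 | 12 | 85 |
| 8 | V9 | 14 | 99 |

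**Checking the plan's own anchors.** The count reproduces two of them: the 3rd dose is at visit 3/week 4 and the 5th at visit 6/week 8. It does not reproduce the third. Visit 8/week 12 is dose 7, and dose 8 falls at visit 9/week 14, which agrees with the protocol's last dose.

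**Window lengths** (end day − start day + 1):

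| Window | By visit label (V8, day 85) | By ordinal (8th dose, day 99) |
|---|---|---|
| Month 1 | 1-28: 28 days | 1-28: 28 days |
| Month 2 | 29-56: 28 days | 29-56: 28 days |
| Month 3 | 57-84: 84 − 57 + 1 = 28 | 57-98: 98 − 57 + 1 = 42 |
| Month 4 | 85-113: 113 − 85 + 1 = 29 | 99-113: 113 − 99 + 1 = 15 |

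Under the ordinal, days 85-98 (14 days) sit in Month 3 instead of Month 4.

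**Can visit tolerance explain the gap?** Protocol Table 3 allows ±3 days per visit. Two boundaries can therefore move a length by at most 6 days. Month 3 is then 36-48 days by ordinal and 22-34 by visit. Month 4 is 9-21 days by ordinal and 29 − 6 = 23 to 29 + 6 = 35 by visit. The ranges do not overlap, so the SAP's allowance for windows other than 28 days does not reconcile the two readings.

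**Missed dose, ordinal reading.** Suppose V4 is skipped and dosing continues. The doses received are V1, V2, V3, V6, V7, V8 and V9. The 5th is then at V7 (day 71), so Month 2 becomes days 29-70 (42 days). No 8th dose exists, so Month 3 has no end and Month 4 no start. Changing 8th to 7th gives Month 4 a start, but at V9 (day 99): Month 4 is again 99-113, or 15 days. Correcting the ordinal removes the contradiction but not the sensitivity to a missed dose.

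**Where length enters directly.** SAP 6.4.4 compares a plain sum of ICS use in each window with a 28-day baseline sum. For illustration only, constant daily use would give 42/28 = 150% of baseline in Month 3 and 15/28 = 54% in Month 4, an apparent 46% decrease. By visit label the figures are 28/28 = 100% and 29/28 = 104%.

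**Week labels.** By the SAP's weekly formula, week 12 is days 78-84 and week 13 starts on day 85. The Month 4 label, which begins at week 12, therefore overlaps the Month 3 label, which ends there.

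**The case against.** The strongest reply is that the damaging reading is the less plausible one. The heading calls these 4-week windows, Month 3 is labelled as ending at week 12, and visit 8/week 12 is printed at both boundaries. Only the ordinal is out of line. This is persuasive as to intent, and it rules out a stronger conclusion that a reader might draw, namely that 14 days of data will change window for every completer. That happens only if the ordinal overrides the visit label.

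A reader might also infer that any missed dose destroys Month 4. The documents do not support that either. By visit label, a patient who skips V4 keeps the V6, V8 and V10 boundaries. Early withdrawal has its own end-of-window note. SAP 6.3.4 uses the last available window for EOT in patients who do not complete treatment. Under protocol Appendix J, a patient who cannot attend because of an outbreak is discontinued from IMP rather than skipping a dose and resuming. The remaining case is a patient who misses a dose, continues and reaches EOT. Protocol 4.4.2 recognises interruption of IMP, but the documents give no frequency.

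The practical effect is also limited. SABA use and hand-held spirometry are daily averages, and awakenings are normalised to 28 days, so length alone does not inflate them. ICS use is an unnormalised sum, but in the protocol Table 1 examples it reaches zero by week 8 in patients without LoAC, so Months 3 and 4 would be near zero on either reading, except in patients starting on higher doses. Both arms are cut the same way, and nothing here shows bias in the treatment contrast. SAP section 7 treats all secondary endpoints as hypothesis-generating.

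These points reduce the consequence but do not remove the contradiction. Normalising corrects for the number of days, not for which days are averaged. No other text says which label governs.

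**Conclusion.** The boundary is wrong as written: the 8th dose and visit 8/week 12 cannot both hold, and the error appears in both the Month 3 and the Month 4 bullets. The evident intention is the visit-8 boundary, with windows of 28 and 29 nominal days. The 42- and 15-day windows, and a missing Month 4 start after a missed dose, are conditional on programming the ordinal. The dosing-day rule leaves that open.

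The scope is the monthly-window secondary analyses: SABA use including EOT, nighttime awakenings, ICS dose and hand-held FEV1/PEF. The primary LoAC analysis does not use these windows, and the weekly windows (weeks 1 to 8) are defined by study day. The day counts assume the nominal visit days in SAP Table 1. The effect on the EOT value assumes that completers' EOT window is Month 4. The point is worth correcting because two programmers following the same SAP could report different key secondary results.

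**What to change.** The minimum change in SAP 6.1.1 is to replace 8th with 7th at the end of Month 3 and the start of Month 4. That removes the contradiction.

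Preferably, drop the ordinals and anchor the boundaries to the V3, V6, V8 and V10 visit dates, using the target study day (29, 57, 85, 113) when a visit or dose is missed. This also settles the missed-dose case. Keep the existing truncation at the end of each patient's treatment period (SAP 1.7 and 6.3.4). Patients who stop IMP still attend later visits, and visit-based windows would otherwise take in off-treatment data. Relabel Month 4 as Weeks 13 to 16.

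The cost is SAP wording only, with no change to conduct or data collection. It should be made before database lock and unblinding, so that the choice of window cannot appear to depend on the results.

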## 6.2. Primary Efficacy Endpoint and Analysis

### 6.2.1. Definition

The primary efficacy endpoint is the proportion of patients who experience loss of asthma control (LoAC) during the treatment period.

LoAC is defined as any one of the following during the treatment period:

- Morning PEF decrease  $\geq 30\%$  from baseline on 2 consecutive days or morning handheld FEV1 decrease  $\geq 20\%$  from baseline on 2 consecutive days
- Increase in SABA/quick-relief medication  $\geq 6$  puffs over baseline use in 24 hours on 2 consecutive days
- Increase in ICS dose  $\geq 4x$  most recent dose
- Systemic corticosteroid use
- Asthma ER visit or hospitalization

LoAC will be determined and recorded by investigator from study sites. A patient who meets criteria for LoAC will discontinue IMP, and resume or increase background asthma controller therapies, but will remain in the study. LoAC events will be treated by the investigator according to local standard of care.

### 6.2.2. Primary Efficacy Analysis

The primary analysis will compare rates of LoAC between treatment groups using logistic regression with fixed effect for treatment, age group (<65 years vs  $\geq 65$  years) and gender, as well as baseline FEV1 and baseline weight as covariates. Patients who withdraw from the study before the week 16 or early terminated the study treatment due to lack of efficacy, LoAC, or an asthma-related adverse event will be analyzed as having experienced LoAC. Patients who withdraw from the study before the week 16 without LoAC or early terminated from the study treatment without experiencing LoAC during the patient's treatment period (Section 1.7) for other reasons will be analyzed as not experiencing LoAC. Asthma-related adverse events will be determined by blinded data reviews prior to the final database lock.

The treatment effect will be tested at a one-sided alpha of 0.1.

The primary analysis will be performed on the ITT analysis set. The rates of LoAC for each treatment group, confidence intervals, and p-value will be displayed.

#### Example SAS code for Logistic Regression

```
PROC GENMOD DATA =name;
  CLASS TRTP AGEGR1 SEX;
  MODEL AVALC = TRTP FEV1 WEIGHT AGEGR1 SEX / DIST=BIN TYPE3;
RUN;
```

Where AVALC denotes the responses with 'yes' for LoAC and 'no' for not having LoAC; TRTP denotes the planned treatment group; AGEGR1 denotes age group; in bold are the SAS key words.

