### 6.2.4. Sensitivity Analysis for the Primary Efficacy Endpoint

As a supplementary analysis, the primary analysis will be repeated on mITT analysis set and the per-protocol analysis set as defined in Section 3.4. In addition, a sensitivity analysis will be performed using multiple imputations method, when there are more than 5% early discontinuations from the study before week 16 due to reasons other than lack of efficacy or asthma-related AEs in either treatment group.

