#### 6.2.4.1. Sensitivity Analysis Using Multiple Imputations

Patients who discontinued the treatment or the study before week 16 without LoAC due to lack of efficacy or asthma-related AEs will be considered as having experienced an LoAC, the same imputation method as used in the primary efficacy analysis.

For patients who discontinued the study before week 16 without LoAC for reasons other than lack of efficacy or due to asthma-related AEs, multiple imputations will be used from a Bernoulli distribution with the probability estimated from a logistic regression model from the observed LoAC data given the treatment group, sex, age group (<65 years vs ≥65 years), baseline FEV1, and baseline weight. A total of 100 datasets will be imputed and each will be analyzed with the logistic regression model the way as for the primary analysis. The final estimates will be obtained using Rubin’s method. The details are as follows:

**Step 1:** Estimate the probabilities for Bernoulli distribution

The SAS procedure in Section 6.2.2 will be used to obtain the probability estimates from a logistic regression model. The following statement will be added to SAS procedure:

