**ODS OUTUT ParameterEstimates=pest;**

Estimates from PROC GENMOD along with patients’ data will be used to calculate the probability, the p used for Bernoulli distribution, for each patient.

Observed data will be duplicated 100 times creating 100 sets of data. In each dataset, the SAS function **RAND(“Bernoulli”, p)** will be used to determine LoAC status (1=having LoAC, 0=not having LoAC) for patients with missing data due to reasons other than lack of efficacy or due to asthma-related AEs.

**Step 2:** Analysis

The 100 sets of data will be analyzed in a manner analogous to the analysis as described in Section 6.2.2 adding a by-statement for imputation to the SAS procedure.

The results from the 100 analyses will be combined using Rubin’s formulae in the following SAS procedure.

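### The example GENMOD code names no event level, and the multiple-imputation step reuses it to obtain P(LoAC); followed literally, it may impute LoAC with probability 1 − p

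*SAP*

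**What the plan says.** SAP 6.2.2 gives example SAS code for the primary logistic regression. The model line is "MODEL AVALC = TRTP FEV1 WEIGHT AGEGR1 SEX / DIST=BIN TYPE3", and the note beneath it reads: "Where AVALC denotes the responses with 'yes' for LoAC and 'no' for not having LoAC". No option says which of the two levels is modelled, and no reference level is named for TRTP.

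SAP 6.2.4 adds a multiple-imputation sensitivity analysis, to be run "when there are more than 5% early discontinuations from the study before week 16" for reasons other than lack of efficacy or asthma-related adverse events, in either arm. Step 1 of SAP 6.2.4.1 states: "The SAS procedure in Section 6.2.2 will be used to obtain the probability estimates from a logistic regression model". The one addition is an ODS statement that saves the parameter estimates. With the patients' data, those estimates "will be used to calculate the probability, the p used for Bernoulli distribution, for each patient". The SAS RAND Bernoulli function with that p "will be used to determine LoAC status (1=having LoAC, 0=not having LoAC").

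**The concern.** The draw is right only if p is the probability of LoAC. The code does not secure that. 'no' sorts before 'yes', so if the procedure models the first-sorted level, the saved coefficients describe the probability of not losing control. Step 1 neither takes the complement of p nor checks its direction.

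The 6.2.2 code is labelled an example, but Step 1 makes the procedure operative and lists what to add to it. Elsewhere the SAP does fix direction in its code: the time-to-event section (6.3.1) defines the censoring code and the numeric treatment values, and the ANCOVA (6.3.2) names placebo as control.

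At stake is the analysis meant to show whether the result survives a different treatment of dropouts. With dropout similar in the two arms, an inverted p places more imputed events on TEV-48574 than on placebo. A real effect could then look fragile to missing data because of coding alone.

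**Working it through.** **Inputs.** LoAC rates 27% (placebo) and 10.8% (TEV-48574), one-sided alpha 0.1, 15% dropout, 62 randomized per arm and 80% power (Protocol 9.1; same figures in SAP 2.4). Trigger above 5% and 100 imputations (SAP 6.2.4 and 6.2.4.1). The share d of each arm that is imputed is not given. It is taken as 5% to 15% and equal in both arms.

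**The plan's own figure.** With the chi-square test named in the protocol and mean rate 0.189:

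n = [1.2816·√(2·0.189·0.811) + 0.8416·√(0.27·0.73 + 0.108·0.892)]² / 0.162² = 51.8, so 52 evaluable per arm; 52/0.85 = 61.2, so 62 randomized. The stated figure reproduces.

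**Effect of the modelled level on p.** SAS was not run. A treatment-only logistic fit in Python to 20,000 simulated patients at the planned rates gave:
- 'yes' modelled: fitted p 0.267 (placebo) and 0.109 (active), odds ratio 0.335.
- 'no' modelled: fitted p 0.733 and 0.891, odds ratio 2.98.

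The two-sided p-value was the same in both fits; only the signs changed.

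**Expected arm rate after imputation.** Correct: (1 − d)·p + d·p = p. Inverted: (1 − d)·p + d·(1 − p).

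- d = 5%: placebo 0.95·0.27 + 0.05·0.73 = 29.3%; active 0.95·0.108 + 0.05·0.892 = 14.7%.
- d = 10%: placebo 0.90·0.27 + 0.10·0.73 = 31.6%; active 0.90·0.108 + 0.10·0.892 = 18.6%.
- d = 15%: placebo 0.85·0.27 + 0.15·0.73 = 33.9%; active 0.85·0.108 + 0.15·0.892 = 22.6%.

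At d = 15%, 62·0.15 = 9.3 patients per arm are imputed. Expected imputed events are 9.3·0.73 = 6.8 (placebo) and 9.3·0.892 = 8.3 (active), instead of 9.3·0.27 = 2.5 and 9.3·0.108 = 1.0.

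**Power.** 5,000 simulated trials, 62 per arm, 100 imputations combined by Rubin's rules, treatment-only log odds ratio with a 0.5 cell correction, dropout completely at random:

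| Imputed per arm | Risk ratio, inverted (correct 0.40) | Odds ratio, inverted (correct 0.33) | Power, correct | Power, inverted |
|---|---|---|---|---|
| 5% | 0.50 | 0.42 | 0.85 | 0.77 |
| 10% | 0.59 | 0.50 | 0.82 | 0.65 |
| 15% | 0.67 | 0.57 | 0.80 | 0.52 |

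With both arms at 27%, the inverted version rejects in 8.1%, 5.8% and 4.6% of trials, against about 10% when coded correctly. With equal shares the error therefore attenuates the effect and does not create false positives.

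**Unequal dropout.** The trigger can be met by one arm alone. If 5% were imputed on placebo and none on active, the inverted rates would be 29.3% and 10.8%, a risk ratio of 0.108/0.293 = 0.37. The bias would then favour TEV-48574.

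**The case against.** The best defence is that the code is only an illustration and the prose is clear. The intended p in SAP 6.2.4.1 comes from a model of the observed LoAC data, and the draw is defined as LoAC status. No sentence supports imputing from the probability of no LoAC, so an inverted run would be a programming error against the plan's text. Step 1 also saves coefficients, not fitted probabilities, so someone must build p for each patient and could notice. The printed code needs expanding in any case: the pooling step reads a dataset, 'diff', that nothing shown creates. And the direction rests on a software default that neither document states; if 'yes' is modelled, nothing goes wrong.

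All of this stands, and it limits the point to what may happen under a literal reading. It does not remove the point, because Step 1 says which procedure to run and what to add, and that instruction leaves the direction of p open.

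A reader might go further and infer that the primary conclusion could be reversed. The documents do not support that. The two-sided (TYPE3) p-value does not depend on which level is modelled. Protocol 9.6.1.3 defines the effect as the odds ratio of TEV-48574 against placebo, the sample-size sections set the alternative as a reduction in LoAC, and SAP 6.2.2 has the arm rates displayed beside the test. An odds ratio near 3 next to rates of 27% and 10.8% would be an evident contradiction. The sign of the treatment coefficient also depends on the unnamed TRTP reference; the fitted probabilities do not.

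**Conclusion.** The point holds as a defect in the instructions for one sensitivity analysis. Assuming that 'no' is modelled and Step 1 is followed literally, equal imputed shares of 5% to 15% move the risk ratio from 0.40 to between 0.50 and 0.67, and cut simulated power from 0.85–0.80 to 0.77–0.52.

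The upper end should not be read as the expected case. The 15% is total planned dropout, while only study discontinuations without LoAC for other reasons are imputed. The analysis runs only above the 5% trigger: 62·0.05 = 3.1, so at least 4 patients in one arm of 62. The simulation omits the model's covariates and takes dropout as completely at random. The primary analysis is affected at most in the sign of its coefficient, which the surrounding text already settles.

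**What to change.** In SAP 6.2.2, write `MODEL AVALC(EVENT='yes') = ...` and name placebo as the reference level for TRTP. Add that the one-sided test is for an odds ratio (TEV-48574/placebo) below 1. In SAP 6.2.4.1 Step 1, state that p is P(LoAC) from that model, and check that the mean fitted p among the observed patients equals their observed LoAC rate.

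The cost is two options in the code and two sentences before database lock. No planned analysis, estimand or sample size changes.
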